The rationale for further exploration of 2 mg/kg and comparable doses of pembrolizumab in solid tumors is based on: 1) similar efficacy and safety of pembrolizumab when dosed at either 2 mg/kg or 10 mg/kg Q3W in melanoma patients, 2) the flat exposure-response relationships of pembrolizumab for both efficacy and safety in the dose ranges of 2 mg/kg Q3W to 10 mg/kg Q3W, 3) the lack of effect of tumor burden or indication on distribution behavior of pembrolizumab (as assessed by the population PK model) and 4) the assumption that the dynamics of pembrolizumab target engagement will not vary meaningfully with tumor type.

The choice of the 200 mg Q3W as an appropriate dose for the switch to fixed dosing is based on simulations performed using the population PK model of pembrolizumab (28) showing that the fixed dose of 200 mg every 3 weeks will provide exposures that 1) are optimally consistent with those obtained with the 2 mg/kg dose every 3 weeks, 2) will maintain individual patient exposures in the exposure range established in melanoma as associated with maximal efficacy response and 3) will maintain individual patients exposure in the exposure range established in melanoma that are well tolerated and safe.

Dexamethasone

Rationale for dose and duration:

Based on our preclinical data, the concentration of DEX required to cause senescence in lung cancer cells was about 100nM (10). This concentration can be achieved using the dose of DEX at 4mg BID for 7-13 days. The effects on senescence by DEX was also directly proportional to the intensity of GR expression. Given intratumor heterogeneity and the problems of using archival tissue to test this biomarker, we are not pre-selecting patients in this initial study. Instead, we will vary the duration of pre-treatment DEX to 7, 10 or 13 days for the run in part of the study, prior to initial dose of pembrolizumab.

There has been no phase I data that has specifically evaluated pre-treatment with dexamethasone prior to pembrolizumab. There is however data that suggest that the 2 should not be administered concurrently (29). We are therefore proposing a wash out period of at least 3 days ($t_{1/2}$ 36-54h) before administration of pembrolizumab. There are not any serious adverse events that appear to overlap between the two agents based on review of published phase I/II/III and data.

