6.0 TREATMENT PLAN

6.1 Drug Administration

6.1.1 Treatment

Both dexamethasone and pembrolizumab are standard medications and will be used from commercial standard supply. The first dose of trial treatment is considered to be first dose of dexamethasone. Trial treatment should begin within 14 days of enrollment.

Table 2: Treatment drugs

Drug	Dose/Potency	Dose Frequency	Route of Administration	Regimen/Treatment Period
Pembrolizumab	200 mg	Q3W	IV infusion	Day 1 of each 21-day cycle

Dexamethasone will be administered orally, prior to each dose of pembrolizumab for 3 cycles in the following cohorts:

Cohort 1: 4 mg BID for 7 days, followed by taper 2 mg BID for 1 day and 1 mg BID and 3 day wash out.

Cohort 2: 4mg BID for 10 days, followed by 2 mg BID for 2 days, 1 mg BID for 1 day and 3 day wash out.

Cohort 3: 4 mg BID for 13 days, 2mg BID for 3 days, 1 mg BID for 1day and 3 day wash out

Pembrolizumab 200 mg (IV) will be administered per institutional standard of care guidelines.

Subjects will be given a pill diary and instructed to complete for each day of administration of Dexamethasone. Missed and/or vomited doses should be recorded on the diary as such. Subjects will be asked to bring their pill diary to each study visit.

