7.2 Treatment Calendar

SCHEDULE OF EVENTS COHORT 1

Procedure	Screening (within 28 days prior to Day 0) ¹	Baseline Day 0	(C1D1)	Lead In C2 and C3	(C2 and 3D1) (± 3Days)	(C4+) (± 3 Days)	EOT	Follow Up ¹
Informed Consent	X							
Medical History	X							
Physical exam	X		X		X	X	X	
Vital Signs	X		X		X	X	X	
ECOG performance status	X		X		X	X	X	
Adverse Events	X		X		X	X	X	X
Concomitant Medications	X		X		X	X	X	X
CBCPD	X		X		X	X	X	
Comp	X		X		X	X	X	
Coagulation (PT/aPTT) ⁷	X							
FDG PET/CT-Chest (VA Ann Arbor) ²	X					X	X	
CT Abdomen/Pelvis ³	X							
Research Blood ⁴		X	X		X			
FLT PET (University of Michigan)		X	X					
Dexamethasone ⁵		X		X	X			
Pembrolizumab ⁶			X		X	X		

¹ Follow Up: Phone call 6 weeks after EOT including any new treatments

² FDG PET/CT-Chest: C4D1 (±7days), then Every 12 weeks (±7days)

³ CT-Abdomen/Pelvis: at screening, C4D1 (±7days), then Every 12 weeks (±7days) **only if disease is present in that area**

⁴ Research Blood: T/TK, SAP, cytokines, chemokines, immune cell subsets; Drawn with 1st FLT PET, 2nd FLT PET, C1D1, C2D1, C3D1 only

⁵ Dexamethasone given orally. Start immediately after FLT PET Day 0 – Day 9. Lead in Day 9-17

⁶ Pembrolizumab given up to 1 year every 21 days

⁷ Only required if clinically indicated or on anticoagulants

SCHEDULE OF EVENTS COHORT 2

Procedure	Screening (within 28 days prior to Day 0) ¹	Baseline Day 0	(C1D1)	Lead In C2 and C3	(C2 and 3D1) (± 3Days)	(C4+) (± 3 Days)	EOT	Follow Up ¹
Informed Consent	X							
Medical History	X							
Physical exam	X		X		X	X	X	
Vital Signs	X		X		X	X	X	
ECOG performance status	X		X		X	X	X	
Adverse Events	X		X		X	X	X	X
Concomitant Medications	X		X		X	X	X	X
CBCPD	X		X		X	X	X	
Comp	X		X		X	X	X	
Coagulation (PT/aPTT) ⁷	X							
FDG PET/CT-Chest (VA Ann Arbor) ²	X					X	X	
CT Abdomen/Pelvis ³	X							
Research Blood ⁴		X	X		X			
FLT PET (University of Michigan)		X	X					
Dexamethasone ⁵		X		X	X			
Pembrolizumab ⁶			X		X	X		

¹ Follow Up: Phone call 6 weeks after EOT including any new treatments

² FDG PET/CT-Chest: C4D1 (±7days), then Every 12 weeks (±7days)

³ CT-Abdomen/Pelvis: at screening, C4D1 (±7days), then Every 12 weeks (±7days) **only if disease is present in that area**

⁴Research Blood: T/TK, SAP, cytokines, chemokines, immune cell subsets; Drawn with 1st FLT PET, 2nd FLT PET, C1D1, C2D1, C3D1 only

⁵ Dexamethasone given orally. Start immediately after FLT PET Day 0 – Day 9. Lead in Day 9-17

⁶Pembrolizumab given up to 1 year every 21 days

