12.0 LABELING, PACKAGING, STORAGE AND RETURN OF CLINICAL SUPPLIES

12.1 Investigational Drugs

The investigator shall take responsibility for and shall take all steps to maintain appropriate records and ensure appropriate supply, storage, handling, distribution and usage of study drug in accordance with the protocol and any applicable laws and regulations.

Dexamethasone is available through commercial supply. It will be administered orally according to study schema.

Pembrolizumab is available through commercial supply. It will be administered intravenously every 21 days per institutional standard policy

Product Name & Potency	Dosage Form
Pembrolizumab 50 mg	Lyophilized Powder for Injection
Pembrolizumab 100 mg/ 4mL	Solution for Injection

Dexamethasone is available through commercial supply and will be administered 7 days prior with 3 days off before each pembrolizumab infusion.

Drug Name:	Dexamethasone
INN:	Dexamethasone
Formulation:	Tablet;

How Supplied:	2mg white, scored tablet 4mg green, scored tablet 6 mg aqua, scored tablet Come in high-density polyethylene bottles or equivalent with child-resistant caps. Patients may receive 1 or more strengths. Each bottle contains 100 tablets
Storage Conditions:	20-25 °C (68 and 77° F) protect from moisture

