14.0 APPENDICES

I. ECOG Performance Status

Grade	Description
0	Normal activity. Fully active, able to carry on all pre-disease performance without restriction.
1	Symptoms, but ambulatory. Restricted in physically strenuous activity, but ambulatory and able to carry out work of a light or sedentary nature (e.g., light housework, office work).
2	In bed <50% of the time. Ambulatory and capable of all self-care, but unable to carry out any work activities. Up and about more than 50% of waking hours.
3	In bed >50% of the time. Capable of only limited self-care, confined to bed or chair more than 50% of waking hours.
4	100% bedridden. Completely disabled. Cannot carry on any self-care. Totally confined to bed or chair.
5	Dead.

* As published in Am. J. Clin. Oncol.: *Oken, M.M., Creech, R.H., Tormey, D.C., Horton, J., Davis, T.E., McFadden, E.T., Carbone, P.P.: Toxicity And Response Criteria Of The Eastern Cooperative Oncology Group. Am J Clin Oncol 5:649-655, 1982.* The Eastern Cooperative Oncology Group, Robert Comis M.D., Group Chair.

II. Common Terminology Criteria for Adverse Events V4.03 (CTCAE)

The descriptions and grading scales found in the revised NCI Common Terminology Criteria for Adverse Events (CTCAE) version 4.0 will be utilized for adverse event reporting. (<https://evs.nci.nih.gov/ftp1/CTCAE/About.html>.)

III Procedure for patients on study

1. Patient will sign consent
2. Patient will have regular standard of care procedures and they will be reviewed and used for eligibility.
3. Patient will be scheduled for baseline FLT PET and FLT PET prior to Pembrolizumab and all future clinic appointments so they know when they will be ahead of time
4. Patient will be called the day before for a reminder of their FLT PET and to start Dexamethasone after FLT PET
5. Patient will go to the University of Michigan for FLT PET and take 1st dose of Dexamethasone immediately afterwards – Coordinator will meet patient for Research blood draw and reimburse patient for this visit (\$25)
6. Patient will be called and reminded to stop taking dexamethasone
7. Patient will be called and reminded about their appointments the next day which are the last FLT PET, visit with [name], cycle 1 of Pembrolizumab infusion
8. Patient will go to the University of Michigan for FLT PET and then come to VA Ann Arbor to begin Pembrolizumab treatment – Patient will be reimbursed to this visit (\$25)

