9. The same thing will happen for the next 2 cycles regarding starting and stopping dexamethasone without the FLT PET
10. Patients will have imaging (FDG-PET and CT-Chest, CT-Abdomen and Pelvis only required if disease is present in that area) at screening, C4D1 (± 7 days), then Every 12 weeks (± 7 days)

IVA. PATIENT'S MEDICATION DIARY COHORT 1 CYCLE 1-3Today's date _____ Agent: **Dexamethasone**

Patient Initials _____ Patient Study ID _____

INSTRUCTIONS TO THE PATIENT:-

- You will take **Dexamethasone orally twice a day, approximately 12 hours apart**
- You should take your capsule(s) at approximately the same time each morning and evening.

Dexamethasone Taper

4mg Dex morning and evenings on Days 10-16; then again on Days 31-37

2mg Dex morning and evenings on Day 17; then again on Day 38

1mg Dex morning and evenings on Day 18; then again on Day 39

Day	Date	Time of Dose		Dexamethasone		Comments	
		AM	PM	_____ mg			
	F	FLT PET @ UM @ _____; Blood Draw; Start Dexamethasone					
		AM	PM	_____mg AM	_____mg PM		
	Sa	AM	PM	_____mg AM	_____mg PM		
	Su	AM	PM	_____mg AM	_____mg PM		
	M	AM	PM	_____mg AM	_____mg PM		
	Tu	AM	PM	_____mg AM	_____mg PM		
	W	AM	PM	_____mg AM	_____mg PM		
	Th	AM	PM	_____mg AM	_____mg PM		
	F	AM	PM	_____mg AM	_____mg PM		
	Sa	AM	PM	_____mg AM	_____mg PM		
	Su	No Dexamethasone					
	M	No Dexamethasone					
	Tu	No Dexamethasone					
1	W	FLT PET @ UM @ _____; Blood Draw; RV w/[name] @ _____; PEMBROLIZUMAB INFUSION (Cycle 1 Day 1 = 1st Dose)					
2	Th						
3	F						
4	Sa						
5	Su						
6	M						
7	Tu						
8	W						
9	Th						
10	F	AM	PM	_____mg AM	_____mg PM		

11	Sa	AM	PM	_____mg AM	_____mg PM
12	Su	AM	PM	_____mg AM	_____mg PM
13	M	AM	PM	_____mg AM	_____mg PM
14	Tu	AM	PM	_____mg AM	_____mg PM
15	W	AM	PM	_____mg AM	_____mg PM
16	Th	AM	PM	_____mg AM	_____mg PM
17	F	AM	PM	_____mg AM	_____mg PM
18	Sa	AM	PM	_____mg AM	_____mg PM
19	Su	No Dexamethasone			
20	M	No Dexamethasone			
21	Tu	No Dexamethasone			
22	W	Blood Draw; RV w/[name] @ _____; PEMBROLIZUMAB INFUSION (Cycle 2 Day 1 = 2nd Dose)			
23	Th				
24	F				
25	Sa				
26	Su				
27	M				
28	Tu				
29	W				
30	Th				
31	F	AM	PM	_____mg AM	_____mg PM
32	Sa	AM	PM	_____mg AM	_____mg PM
33	Su	AM	PM	_____mg AM	_____mg PM
34	M	AM	PM	_____mg AM	_____mg PM
35	Tu	AM	PM	_____mg AM	_____mg PM
36	W	AM	PM	_____mg AM	_____mg PM
37	Th	AM	PM	_____mg AM	_____mg PM
38	F	AM	PM	_____mg AM	_____mg PM
39	Sa	AM	PM	_____mg AM	_____mg PM
40	Su	No Dexamethasone			
41	M	No Dexamethasone			

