35	Tu	AM	PM	____ mg AM	____ mg PM		
36	W	AM	PM	____ mg AM	____ mg PM		
37	Th	AM	PM	____ mg AM	____ mg PM		
38	F	AM	PM	____ mg AM	____ mg PM		
39	Sa	AM	PM	____ mg AM	____ mg PM		
40	Su	No Dexamethasone					
41	M	No Dexamethasone					
42	Tu	No Dexamethasone					
43	W	Blood Draw; RV w/[name] @ _____; PEMBROLIZUMAB INFUSION (Cycle 3 Day 1 =3rd Dose)					

IVC. PATIENT'S MEDICATION DIARY COHORT 3 CYCLE 1 – 3Today's date _____ Agent: **Dexamethasone**

Patient Initials _____ Patient Study ID _____

INSTRUCTIONS TO THE PATIENT:-

- You will take **Dexamethasone orally twice a day, approximately 12 hours apart**
- You should take your capsule(s) at approximately the same time each morning and evening.

Dexamethasone Taper

4mg Dex morning and evenings on Days 9-21; then again on Days 37-49

2mg Dex morning and evenings on Days 22-24; then again on Days 50-52

1mg Dex morning and evenings on Day 25; then again on Day 53

Day	Date	Time of Dose		Dexamethasone		Comments	
		AM	PM	_____ mg	_____ mg		
	TH	FLT PET @ UM @ _____; Blood Draw; Start Dexamethasone					
		AM	PM	_____ mg AM	_____ mg PM		
	F	AM	PM	_____ mg AM	_____ mg PM		
	Sa	AM	PM	_____ mg AM	_____ mg PM		
	Su	AM	PM	_____ mg AM	_____ mg PM		
	M	AM	PM	_____ mg AM	_____ mg PM		
	Tu	AM	PM	_____ mg AM	_____ mg PM		
	W	AM	PM	_____ mg AM	_____ mg PM		
	Th	AM	PM	_____ mg AM	_____ mg PM		
	F	AM	PM	_____ mg AM	_____ mg PM		
	Sa	AM	PM	_____ mg AM	_____ mg PM		
	Su	AM	PM	_____ mg AM	_____ mg PM		
	M	AM	PM	_____ mg AM	_____ mg PM		
	Tu	AM	PM	_____ mg AM	_____ mg PM		
	W	AM	PM	_____ mg AM	_____ mg PM		
	Th	AM	PM	_____ mg AM	_____ mg PM		
	F	AM	PM	_____ mg AM	_____ mg PM		
	Sa	AM	PM	_____ mg AM	_____ mg PM		
	Su	No Dexamethasone					
	M	No Dexamethasone					
	Tu	No Dexamethasone					
1	W	FLT PET @ UM @ _____; Blood Draw; RV w/[name] @ _____;					
		PEMBROLIZUMAB INFUSION (Cycle 1 Day 1 = 1st Dose)					
2	Th						

3	F						
4	Sa						
5	Su						
6	M						
7	Tu						
8	W						
9	Th	AM	PM	____ mg AM	____ mg PM		
10	F	AM	PM	____ mg AM	____ mg PM		
11	Sa	AM	PM	____ mg AM	____ mg PM		
12	Su	AM	PM	____ mg AM	____ mg PM		
13	M	AM	PM	____ mg AM	____ mg PM		
14	Tu	AM	PM	____ mg AM	____ mg PM		
15	W	AM	PM	____ mg AM	____ mg PM		
16	Th	AM	PM	____ mg AM	____ mg PM		
17	F	AM	PM	____ mg AM	____ mg PM		
18	Sa	AM	PM	____ mg AM	____ mg PM		
19	Su	AM	PM	____ mg AM	____ mg PM		
20	M	AM	PM	____ mg AM	____ mg PM		
21	Tu	AM	PM	____ mg AM	____ mg PM		
22	W	AM	PM	____ mg AM	____ mg PM		
23	Th	AM	PM	____ mg AM	____ mg PM		

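### The ±3-day window on C2D1 and C3D1 conflicts with the minimum 3-day dexamethasone wash-out before each pembrolizumab infusion, and no text says which rule governs

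*Combined protocol and SAP*

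**What the plan says.** **Visit window.** Each of the three schedules in section 7.2 has a column headed "C2 and 3D1) (± 3Days", and pembrolizumab is marked in it. The separate column for the cycle 2 and 3 lead-in carries no window, and neither does C1D1.

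**Wash-out.** Section 4.2.2 refers to data against giving the two drugs together and concludes: "We are therefore proposing a wash out period of at least 3 days". Section 6.1.1 ends each cohort's regimen with the same gap; for Cohort 1 it reads "followed by taper 2 mg BID for 1 day and 1 mg BID and 3 day wash out". Section 12.1 says dexamethasone "will be administered 7 days prior with 3 days off before each pembrolizumab infusion".

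**Printed days.** The Cohort 1 and Cohort 2 diaries (Appendix IVA and IVB) both end each lead-in with "1mg Dex morning and evenings on Day 18; then again on Day 39". The entry "PEMBROLIZUMAB INFUSION (Cycle 2 Day 1 = 2nd Dose" stands at Day 22, and the third dose at Day 43. The Cohort 3 diary (Appendix IVC) has "1mg Dex morning and evenings on Day 25; then again on Day 53", with infusions on Days 29 and 57. All these infusion days are Wednesdays.

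**Scheduling.** Appendix III, item 3, books the FLT-PET scans and "all future clinic appointments so they know when they will be ahead of time". Item 6 has the site telephone the patient to stop dexamethasone, and item 9 repeats the start and stop procedure for the next two cycles.

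**The concern.** The diaries leave exactly the minimum wash-out, and the calendar lets the infusion move earlier by up to the whole of it. Coordinators commonly judge by the calendar whether a visit is acceptable. Here it shows as in window a date that three other sections rule out.

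The wash-out is the protocol's own safeguard against giving pembrolizumab too close to a steroid. The exposed data are the second and third infusions, which feed the secondary response rate, and the research bloods at C2D1 and C3D1. Those bloods enter the marker trajectories of section 11.1 and the later immune time points of section 11.4. A blood drawn after one or two free days would be analysed alongside bloods drawn after three.

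**Working it through.** **Inputs**, from the diaries in Appendix IVA to IVC, with the shift range from section 7.2:

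| Cohort | Visit | Lead-in starts | Last dexamethasone day | Infusion day |
|---|---|---|---|---|
| 1 | C2D1 | 10 | 18 | 22 |
| 1 | C3D1 | 31 | 39 | 43 |
| 2 | C2D1 | 6 | 18 | 22 |
| 2 | C3D1 | 27 | 39 | 43 |
| 3 | C2D1 | 9 | 25 | 29 |
| 3 | C3D1 | 37 | 53 | 57 |

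**Formula.** Free days = (infusion day + shift) − last dexamethasone day − 1.

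**Reproducing the plan's figure (shift 0).** Cohorts 1 and 2: 22 − 18 − 1 = 3 and 43 − 39 − 1 = 3. Cohort 3: 29 − 25 − 1 = 3 and 57 − 53 − 1 = 3. The stated three-day wash-out is met exactly.

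**Across the window.** The result is the same for both visits in every cohort:

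| Shift (days) | −3 | −2 | −1 | 0 | +1 | +2 | +3 |
|---|---|---|---|---|---|---|---|
| Weekday | Sun | Mon | Tue | Wed | Thu | Fri | Sat |
| Free days | 0 | 1 | 2 | 3 | 4 | 5 | 6 |

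Every early shift falls below the minimum and every late shift meets it.

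**When both rules can be met.** The lead-in can move with the visit, but only if the change is made before the lead-in begins. Lead-in start to infusion is 22 − 10 = 12 days in Cohort 1, 22 − 6 = 16 in Cohort 2 and 29 − 9 = 20 in Cohort 3. C3D1 gives the same: 43 − 31 = 12, 43 − 27 = 16, 57 − 37 = 20. Once dexamethasone has started, bringing the infusion forward must shorten either the wash-out or the course.

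**Check against footnote 5 of the calendars.** The footnote gives the lead-in as Days 9 to 17. Taken literally against a Day 22 infusion, that leaves 22 − 17 − 1 = 4 free days on time, then 3, 2 and 1 at one, two and three days early. On that reading the breach starts at two days early. If C1D1 is counted as Day 0, the infusion is on Day 21 and 21 − 17 − 1 = 3, which agrees with the Cohort 1 diary. The footnote spans 17 − 9 + 1 = 9 days. That fits Cohort 1 (7 + 1 + 1 = 9) but cannot hold the courses of Cohort 2 (10 + 2 + 1 = 13) or Cohort 3 (13 + 3 + 1 = 17), although it is printed for both. The diaries are therefore the better basis.

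**What is not exposed.** C1D1 has no printed window, so the second FLT-PET scan and the cycle 0 to cycle 1 marker changes keep their timing. From cycle 4 there is no lead-in: section 6.1.1 limits dexamethasone to three cycles, and the diaries end at C3D1.

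**The case against.** The strongest reply is that the wash-out already governs. Sections 4.2.2, 6.1.1 and 12.1 set dexamethasone timing relative to the infusion, and a general visit-window heading does not authorise dosing that breaks a stated minimum. The site also manages the dates actively: appointments are booked ahead, patients are telephoned to stop dexamethasone, and the diary has a date column to fill in. On this view only a cross-reference is missing.

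Much of this stands. A reader might infer that the plan permits pembrolizumab before the wash-out is complete, or that nothing in it limits the window. The documents do not support that, because the three-day minimum is stated for each infusion. What remains is a conflict between two written rules with no order of precedence. Advance booking and telephone calls make a short-notice change less likely. They do not tell staff what to do when a visit is brought forward after the lead-in has begun.

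It is also fair to say that the consequence is small. Section 4.2.1 describes the lymphocyte effect as quickly reversible and notes that standard front-line treatment already includes three days of dexamethasone at the same dose around chemo-immunotherapy. The committee in section 13.4 reviews protocol deviations, so a short wash-out could be noticed, although the visit itself would be in window.

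**Conclusion.** The conflict is real and minor. On the printed dexamethasone days, any early C2D1 or C3D1 infusion breaks the minimum wash-out, leaving 2, 1 or 0 free days instead of 3. The last case is unlikely because it falls on a Sunday. The conclusion assumes that the diary days are followed and that the lead-in is not moved with the visit; the documents neither require nor rule out moving it.

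Two stronger inferences are not supported. The first is that the primary analysis is compromised: the FLT-PET endpoint and the stage decisions rest on scans up to C1D1, which this window does not touch. The second is that a shorter wash-out would lower the response rate: the documents link no residual dexamethasone level to response. They also give no basis for estimating how often visits would be early, so no size can be put on any effect on the response rate or the exploratory markers.

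**What to change.** In all three calendars, change the C2D1 and C3D1 window to 0 to +3 days. The wash-out is then always 3 to 6 free days.

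Alternatively, keep ±3 days and add a footnote with two parts: pembrolizumab is given only after at least three full dexamethasone-free days, and if a visit is brought forward, the lead-in start moves forward by the same number of days.

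Either is a small text edit in three tables. The cost of the first is less scheduling flexibility at two visits. The second keeps early visits but needs the change to be made before the lead-in starts.

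As a separate clerical correction, footnote 5 should give each cohort's own diary days: Days 10–18 and 31–39 for Cohort 1, Days 6–18 and 27–39 for Cohort 2, and Days 9–25 and 37–53 for Cohort 3.

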⁷Only required if clinically indicated or on anticoagulants

SCHEDULE OF EVENTS COHORT 3

Procedure	Screening (within 28 days prior to Day 0) ¹	Baseline Day 0	(C1D1)	Lead In C2 and C3	(C2 and 3D1) (± 3Days)	(C4+) (± 3 Days)	EOT	Follow Up ¹
Informed Consent	X							
Medical History	X							
Physical exam	X		X		X	X	X	
Vital Signs	X		X		X	X	X	
ECOG performance status	X		X		X	X	X	
Adverse Events	X		X		X	X	X	X
Concomitant Medications	X		X		X	X	X	X
CBCPD	X		X		X	X	X	
Comp	X		X		X	X	X	
Coagulation (PT/aPTT) ⁷	X							
FDG PET/CT-Chest (VA Ann Arbor) ²	X					X	X	
CT Abdomen/Pelvis ³	X							
Research Blood ⁴		X	X		X			
FLT PET (University of		X	X					
Dexamethasone ⁵		X		X	X			
Pembrolizumab ⁶			X		X	X		

¹ Follow Up: Phone call 6 weeks after EOT including any new treatments

² FDG PET/CT-Chest: C4D1 (±7days), then Every 12 weeks (±7days)

³ CT-Abdomen/Pelvis: at screening, C4D1 (±7days), then Every 12 weeks (±7days) **only if disease is present in that area**

⁴ Research Blood: T/TK, SAP, cytokines, chemokines, immune cell subsets; Drawn with 1st FLT PET, 2nd FLT PET, C1D1, C2D1, C3D1 only

⁵ Dexamethasone given orally. Start immediately after FLT PET Day 0 – Day 9. Lead in Day 9-17

⁶ Pembrolizumab given up to 1 year every 21 days

⁷ Only required if clinically indicated or on anticoagulants

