42	Tu	No Dexamethasone			
43	W	Blood Draw; RV w/[name] @ _____; PEMBROLIZUMAB INFUSION (Cycle 3 Day 1 =3rd Dose)			

IVB. PATIENT'S MEDICATION DIARY COHORT 2 CYCLE 1-3Today's date _____ Agent: **Dexamethasone**

Patient Initials _____ Patient Study ID _____

INSTRUCTIONS TO THE PATIENT:-

- You will take **Dexamethasone orally twice a day, approximately 12 hours apart**
- You should take your capsule(s) at approximately the same time each morning and evening.

Dexamethasone Taper

4mg Dex morning and evenings on Days 6-15; then again on Days 27-36

2mg Dex morning and evenings on Day 16-17; then again on Day 37-38

1mg Dex morning and evenings on Day 18; then again on Day 39

Day	Date	Time of Dose		Dexamethasone		Comments	
		AM	PM	_____ mg	_____ mg		
	M	FLT PET @ UM @ _____; Blood Draw; Start Dexamethasone					
		AM	PM	_____ mg AM	_____ mg PM		
	Tu	AM	PM	_____ mg AM	_____ mg PM		
	W	AM	PM	_____ mg AM	_____ mg PM		
	Th	AM	PM	_____ mg AM	_____ mg PM		
	F	AM	PM	_____ mg AM	_____ mg PM		
	Sa	AM	PM	_____ mg AM	_____ mg PM		
	Su	AM	PM	_____ mg AM	_____ mg PM		
	M	AM	PM	_____ mg AM	_____ mg PM		
	Tu	AM	PM	_____ mg AM	_____ mg PM		
	W	AM	PM	_____ mg AM	_____ mg PM		
	Th	AM	PM	_____ mg AM	_____ mg PM		
	F	AM	PM	_____ mg AM	_____ mg PM		
	Sa	AM	PM	_____ mg AM	_____ mg PM		
	Su	No Dexamethasone					
	M	No Dexamethasone					
	Tu	No Dexamethasone					
1	W	FLT PET @ UM @ _____; Blood Draw; RV w/[name] @ _____; PEMBROLIZUMAB INFUSION (Cycle 1 Day 1 = 1st Dose)					
2	Th						
3	F						
4	Sa						
5	Su						
6	M	AM	PM	_____ mg AM	_____ mg PM		
7	Tu	AM	PM	_____ mg AM	_____ mg PM		

8	W	AM	PM	____ mg AM	____ mg PM		
9	Th	AM	PM	____ mg AM	____ mg PM		
10	F	AM	PM	____ mg AM	____ mg PM		
11	Sa	AM	PM	____ mg AM	____ mg PM		
12	Su	AM	PM	____ mg AM	____ mg PM		
13	M	AM	PM	____ mg AM	____ mg PM		
14	Tu	AM	PM	____ mg AM	____ mg PM		
15	W	AM	PM	____ mg AM	____ mg PM		
16	Th	AM	PM	____ mg AM	____ mg PM		
17	F	AM	PM	____ mg AM	____ mg PM		
18	Sa	AM	PM	____ mg AM	____ mg PM		
19	Su	No Dexamethasone					
20	M	No Dexamethasone					
21	Tu	No Dexamethasone					
22	W	Blood Draw; RV w/[name] @ _____; PEMBROLIZUMAB INFUSION (Cycle 2 Day 1 = 2nd Dose)					
23	Th						
24	F						
25	Sa						
26	Su						
27	M	AM	PM	____ mg AM	____ mg PM		
28	Tu	AM	PM	____ mg AM	____ mg PM		
29	W	AM	PM	____ mg AM	____ mg PM		
30	Th	AM	PM	____ mg AM	____ mg PM		
31	F	AM	PM	____ mg AM	____ mg PM		
32	Sa	AM	PM	____ mg AM	____ mg PM		
33	Su	AM	PM	____ mg AM	____ mg PM		
34	M	AM	PM	____ mg AM	____ mg PM		

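### The 7.2 schedules give all three cohorts the same dexamethasone days, too few for cohorts 2 and 3, and cohort 3's pembrolizumab cycle is stated as both 21 and 28 days

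*Combined protocol and SAP*

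**What the plan says.** **Dexamethasone days.** Section 7.2 has one schedule per cohort. Footnote 5 is identical in each: "Start immediately after FLT PET Day 0 – Day 9. Lead in Day 9-17". It gives no dose and no taper.

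Section 6.1.1 gives a different course for each cohort. Cohort 1 has 7 full-dose days and a short taper. The others read "Cohort 2: 4mg BID for 10 days, followed by 2 mg BID for 2 days, 1 mg BID for 1 day" and "Cohort 3: 4 mg BID for 13 days, 2mg BID for 3 days, 1 mg BID for 1day and 3 day wash out". All three end with three days off before pembrolizumab.

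The diaries (Appendix IV) follow 6.1.1. Their full-dose days for the later lead-ins are "4mg Dex morning and evenings on Days 10-16; then again on Days 31-37" (cohort 1), "4mg Dex morning and evenings on Days 6-15; then again on Days 27-36" (cohort 2) and "4mg Dex morning and evenings on Days 9-21; then again on Days 37-49" (cohort 3), each followed by its taper.

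Three other places add to the confusion:

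- Section 12.1 describes a single 7-day course for everyone.
- Section 2.1 ends the last cohort's full dose on Day 13 in one paragraph and on Day 14 in the next.
- Appendix III has patients telephoned to stop dexamethasone, and names no day.

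**Cohort 3's cycle.** The synopsis gives 28 days, and the cohort 3 diary puts pembrolizumab on Days 1, 29 and 57. Table 2 has "Day 1 of each 21-day cycle" with no exception for cohort 3. Footnote 6 of the cohort 3 schedule and section 12.1 also give 21 days, and 2.1 describes a cycle as 21 days.

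**The concern.** Duration of dexamethasone is the only thing that separates the cohorts. Section 11.4 makes the primary objective the shortest duration that produces an FLT-PET response, and 11.1 carries the selected duration into the later stages. The second FLT-PET, which determines response, directly follows the initial course. If staff took the stop day from footnote 5, patients in cohorts 2 and 3 would be scanned after a shorter course than their cohort label says.

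The schedule is also a likely place to look for that day. The diaries do not number the days of the initial course, their milligram fields are blank, and their printed dose instructions cover only the later lead-ins. Section 2.1 numbers only the full-dose days. Footnote 5 is therefore the only text that puts a numbered end on the initial course as a whole.

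For cohort 3 the cycle length also fixes how soon dexamethasone restarts after an infusion.

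**Working it through.** **Inputs.** Days at 4, 2 and 1 mg twice daily come from 6.1.1. The single 1 mg day in cohort 1 comes from its diary, because 6.1.1 gives no count for that step. The wash-out is 3 days.

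**Dosing days** = full-dose days + taper days:

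- Cohort 1: 7 + 1 + 1 = 9
- Cohort 2: 10 + 2 + 1 = 13
- Cohort 3: 13 + 3 + 1 = 17

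The unnumbered initial-course rows of the three diaries also count to 9, 13 and 17.

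**Footnote 5.** Day 0 to 9, read inclusively, is 10 days. Day 9 to 17 is 17 − 9 + 1 = 9 days.

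| Cohort | Dosing days | Initial course, footnote minus plan | Later lead-in, footnote minus plan |
|---|---|---|---|
| 1 | 9 | 10 − 9 = +1 | 9 − 9 = 0 |
| 2 | 13 | 10 − 13 = −3 | 9 − 13 = −4 |
| 3 | 17 | 10 − 17 = −7 | 9 − 17 = −8 |

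**Could day numbering explain it?** In cohort 1, yes for the lead-in: Days 9–17 counted from zero are the diary's Days 10–18. In cohorts 2 and 3, no, because moving the origin does not change the length of a window. The 9-day lead-in is shorter than the full-dose phase alone (10 and 13 days). The 10-day initial window equals cohort 2's full-dose phase only if the taper is left out, and it is too short for cohort 3's.

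**Correct lead-in windows.** In a cycle of L days with d dosing days, the lead-in runs from Day L − 3 − d + 1 to Day L − 3:

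- Cohort 1, L = 21: Day 21 − 3 − 9 + 1 = 10, to Day 18
- Cohort 2, L = 21: Day 21 − 3 − 13 + 1 = 6, to Day 18
- Cohort 3, L = 28: Day 28 − 3 − 17 + 1 = 9, to Day 25

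These reproduce the diaries' first lead-ins. The second lead-ins agree after subtracting one cycle: 31 − 21 = 10 to 39 − 21 = 18; 27 − 21 = 6 to 39 − 21 = 18; 37 − 28 = 9 to 53 − 28 = 25.

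**Cohort 3's cycle.** The diary gives 29 − 1 = 28 and 57 − 29 = 28 days. On 21 days the regimen still fits (17 + 3 = 20), but dexamethasone would start on Day 21 − 3 − 17 + 1 = 2. That is 1 day after pembrolizumab, against 8 days after it on the 28-day cycle.

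**How often cohort 2 or 3 is reached.** I take 11.1's cohorts A to C as cohorts 1 to 3, with 5 patients each, and assume the same true response rate in every cohort.

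- Under 11.1 the next cohort opens if at most 1 of 5 responds. At a 60% rate, 0.4⁵ + 5 × 0.6 × 0.4⁴ = 0.0102 + 0.0768 = 0.087. At 30%, 0.7⁵ + 5 × 0.3 × 0.7⁴ = 0.168 + 0.360 = 0.528.
- Cohort 3 opens with the square of these: 0.008 and 0.279.
- Cohort 2 or 3 is selected with probability 0.087 × 0.913 + 0.0076 × 0.913 = 0.086 at 60%, and 0.528 × 0.472 + 0.279 × 0.472 = 0.381 at 30%.
- Under 2.1's wording, where the next cohort opens only if nobody responds, cohort 2 opens with probability 0.010 and 0.168.

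**The case against.** The strongest reply is that this is a copying slip with safeguards around it. Section 6.1.1 is the treatment section and is explicit for each cohort. Each patient holds a cohort-specific diary with a row per day, marked days without dexamethasone and a marked row for the second FLT-PET. Section 6.1.1 also requires it to be filled in: "Subjects will be given a pill diary and instructed to complete for each day of administration of Dexamethasone". Both FLT-PET visits are booked in advance under Appendix III. Staff would have to prefer a footnote without dose or taper over all of this. That stands, and it limits the practical risk. It does not make the point merely clerical: the footnote is an operative dosing instruction on the variable under test, and nothing says which text prevails.

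A reader might infer more than the documents support:

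- *That exposure before the primary scan would fall by a known amount, or the Dex-free gap would lengthen by a known number of days.* A milligram figure needs a taper that the footnote does not give. A gap in days needs the stop day from the footnote and the scan day from the diary.
- *That the FLT-PET response rate would be biased.* Nothing in the documents allows that effect to be estimated. The probabilities above assume that duration makes no difference, so they describe reach and not bias.
- *That a 21-day cycle breaks the wash-out in cohort 3.* It does not. Section 4.2.2 asks for at least 3 days before pembrolizumab, which 17 + 3 = 20 days allows, and no minimum gap after it is set.
- *That cohort 1's dosing is wrong too.* The difference there is at most one day.

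**Conclusion.** The point holds and should be fixed, but it is limited in reach. For cohorts 2 and 3, footnote 5 contradicts 6.1.1 and the diaries by 3 and 7 days in the initial course and by 4 and 8 days in the later lead-ins, counting Day 0–9 inclusively. Cohort 3's cycle length is contradictory, 28 against 21 days; this cannot affect the primary FLT-PET, which precedes the first cycle.

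The intended regimen is recoverable: the synopsis, 6.1.1 and the diaries agree on 7, 10 and 13 full-dose days. Sample size, type I error and power do not depend on any of this. Harm needs two things together: staff following the footnote, and cohort 2 or 3 opening. At the 60% rate the trial hopes for, cohort 2 opens with probability 0.087 under 11.1. At the 30% null rate the figure is 0.528, so the text matters most when cohort 1 disappoints.

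**What to change.** Make footnote 5 cohort-specific and state both day origins:

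| Cohort | Initial course (baseline FLT-PET = Day 0) | C1D1 and second FLT-PET, same count | Lead-ins for C2 and C3 (preceding pembrolizumab = Day 1) |
|---|---|---|---|
| 1 | Day 0–8 | Day 12 | Days 10–18 of 21 |
| 2 | Day 0–12 | Day 16 | Days 6–18 of 21 |
| 3 | Day 0–16 | Day 20 | Days 9–25 of 28 |

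Three Dex-free days follow each course.

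In Appendix III, give the last dexamethasone day twice: baseline Day 8, 12 or 16 for the initial course, and cycle Day 18, 18 or 25 for the later ones. They must be kept apart, because cycle Day 12 in cohort 2 and cycle Day 16 in cohort 3 are full-dose days.

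State cohort 3's 28-day cycle for the dexamethasone cycles in Table 2, footnote 6, 12.1 and 2.1. Make the duration in 12.1 cohort-specific, and change Days 1–14 in 2.1 to Days 1–13.

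This is a text amendment with re-issued site schedules; it needs no extra patients or procedures.

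Two safety corrections are separate from this point and do not add to its weight. The AST/ALT/bilirubin row of Table 4 refers to a section 6.2.3 that does not exist and to rucaparib, which is not in this trial. It should carry pembrolizumab hepatotoxicity grades and actions, which is clinical content and needs clinical review. The weekly blood tests that 6.3 already requires during dexamethasone should be shown in the 7.2 calendars.
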